**Data analysis:**

[figure not shown]
Data will be assessed for normality and expressed as means  $\pm$  SE or median(range) if not normally distributed. Images will be coded and analysed blind as to allocation to avoid any bias in analysis. Measurements of the gastric emptying will be performed by manually drawing the region of interest on each slice using Analyze9 software (Biomedical Imaging Resource, Mayo Foundation, Rochester, MN, USA) and summing across all the slices to determine the total volume at each time point. In particular the gastric volumes will be analysed distinguishing the contents and the gas. The total gastric volume is the sum of the contents and the gas.

The University will assess small bowel water content from images acquired using the RARE sequences as previously validated. Colonic volumes will be assessed coronal dual echo fast field echo sequence.

The longitudinal relaxation time T1 in the ascending colon and, separately, in the descending colon will be measured using a single slice balanced Turbo Field Echo (bTFE) sequence with a preparatory 180 degrees inversion pulse applied before acquiring the imaging data . Data will be acquired from 8 different inversion times (TI) (time between inversion pulse and imaging pulses) ranging from 25 - 4925 ms. There will be a 10 second gap between each acquisition to allow the system to return to equilibrium. Small regions of interest will be drawn on the resulting images to calculate the mean signal intensity for the region at each different TI or TE. Care will be taken to exclude areas of gas or bowel wall. The data will then be fitted to a model of the signal evolution of the tissue after application of all the preparation and imaging pulses to determine the relaxation times.

The figure below shows the same example but for a T1 recovery curve with the fit to the data

shown as well on the right.

T1 colon data sets will be processed using custom written software in IDL® (Research systems Inc, Boulder, CO) to generate a region of interest in the ascending colon chyme avoiding small 'pockets' of free water (high intensity signal) if present. Then using the mean of this region at all the different echo times to calculate the T1 of the tissue using an in-house program.

Transit will be expressed as WAPS at 24hours (WAPS24) of the 5 markers and converted to transit time in hours using a nomogram (Figure 4) based on previous validation studies.

#### **MRI motility measurement:**

Cine bTFE data will be acquired over 5-10 minutes. An observer will draw a line along the main axis of the AC which will be used to create a number of lines at 90° to this axis. These lines will be automatically propagated through the time series using the deformation fields from the non-rigid registration of the images performed by Motilent. The resulting time series of line lengths will be smoothed to enable measurement of a Motility Index.

#### **Power and statistical analysis:**

Our pilot data with a standard laxative dose of ispaghula 7g t.d.s. showed a change of T1 AUC 0-360 of mean (SD) 88 ( 55) sec.min . Using this data we calculate that n=15 healthy volunteers will give us >90% power to detect such a difference. Statistical analysis will be carried out using Prism 5 (GraphPad Software Inc.). All data will be tested for normality using the Shapiro-Wilk's Test. Two-way analysis of variance (ANOVA) will be used to assess the significance of differences over time, followed by post-hoc tests corrected for multiple-comparison. Paired comparisons will be performed using two-tailed Student's t test for normal, and two-tailed Wilcoxon's test for non-normal data. A p-value < 0.05 will be considered to be statistically significant.

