**Background:**

Chronic constipation affects approximately 17% of the population worldwide and remains an important unmet need since patients are currently often dissatisfied with treatment. Current treatments which stimulate propulsive colonic motility or osmotic laxatives are successful in increasing stool frequency but are often associated with bloating, cramps and abdominal discomfort. Furthermore, such powerful treatments taken intermittently often create abnormal colonic contents and may result in alternation between diarrhoea and no stools. Many patients would benefit from a less powerful treatment which could be taken daily.

Kiwifruit offer such an alternative and have been shown to increase stool volume and frequency. The mode of action however is unclear. Kiwi is 3% fibre (approximately 1/3 insoluble) and contains around 3% nonstarch polysaccharide including pectins, hemicellulose and cellulose, with high water holding capacity 1.5 times that of ispaghula, a commonly used laxative. Two kiwifruit (150g) contain approximately 6.2gm of glucose and 6.5g fructose. The predominant protein is actinidin a cysteine protease. There are also a number of amines including serotonin and its precursor tryptophan, though these are present in only small amounts (serotonin 0.6g/100g). An unusual component is microcrystalline calcium oxalate monohydrate called rafides. While these dissolve in an acid pH it is unknown to what extent these would escape intact into the small intestine where their action might well excite a protective secretory response in enterocytes. Pig studies indicate that while the soluble component of kiwi fibre is well digested in the small bowel the insoluble component passes largely intact into the colon. Fermentation by microbiota lead to increases in ileal and faecal SCFAs.

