**Methodology:**

We will compare the effect of 3 days of 2 kiwifruit b.d vs placebo (28 gm maltodextrin drink providing 120kcal equal to that of 2 kiwifruit) daily.

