#### **Primary endpoint:**

Effect of Kiwifruit on Ascending colon T1 area under curve from time 0-420.

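### Is n=15 too small because it is sized on the ispaghula effect rather than on a kiwifruit effect?

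*Combined protocol and SAP*

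**What the plan says.** All of this is in the combined protocol and SAP.

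- **Power and statistical analysis.** The planning input is a pilot result: "Our pilot data with a standard laxative dose of ispaghula 7g t.d.s. showed a change of T1 AUC 0-360 of mean (SD) 88", SD 55, in sec.min. From it, "we calculate that n=15 healthy volunteers will give us >90% power to detect such a difference". The same section gives a two-tailed paired t test (Wilcoxon if the data are not normal) and a 0.05 threshold.
- **Primary endpoint.** "Effect of Kiwifruit on Ascending colon T1 area under curve from time 0-420". The window is 60 minutes longer than the pilot's.
- **Methodology.** "We will compare the effect of 3 days of 2 kiwifruit b.d vs placebo", in the two-way cross-over described under Study Design.
- **Background.** Kiwifruit is described as 3% fibre, about one third of it insoluble, "with high water holding capacity 1.5 times that of ispaghula". Two fruit weigh 150 g. The section also mentions an ispaghula study at 3.5 g three times daily, whereas the power section gives 7 g three times daily.

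No section states an expected kiwifruit effect on T1 or a smallest difference of interest.

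**The concern.** A sample size should be tied to the effect of the product under test. Here the effect comes from a different product at what the plan calls a standard laxative dose, and nothing says why kiwifruit should match it. Three things in the Background seem to argue against a full carry-over:

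- **Fibre.** Four fruit a day supply far fewer grams of fibre than 21 g of ispaghula.
- **Strength.** The text introduces kiwifruit right after saying "Many patients would benefit from a less powerful treatment which could be taken daily", which can be read as ranking it below ispaghula.
- **Colonic water.** The effect of kiwifruit on colonic water, which T1 reflects, is described as unclear.

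If the kiwifruit effect were much smaller than 88 sec.min, 15 volunteers might miss it. The stated decision rule is a p-value threshold with no confidence interval, so a non-significant result might then be taken as absence of effect.

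**Working it through.** **Inputs.** Mean change 88 and SD 55 sec.min, n=15, two-sided 5%, paired t test (Power and statistical analysis). The SD is attached to a change, so it is read as the SD of paired differences; the text does not say so outright.

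**1. The plan's own figure.** Standardised effect 88/55 = 1.6. Noncentrality 1.6 × √15 = 6.20 on 14 df. Power = 99.99%. Seven volunteers would give 93.8% and six 87.5%. If 55 were instead a per-visit SD with zero correlation, the SD of differences would be 55 × √2 = 77.8 and power 98%. The claim of more than 90% holds either way.

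**2. Reserve at n=15, SD 55.** 90% power needs a difference of 49.5 sec.min (49.5/88 = 56%). 80% power needs 42.8 sec.min (49%).

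**3. Window.** If effect and SD both scale by 420/360 = 1.167, their ratio and the power do not change. The mismatch between 0-360 and 0-420 has no material effect here.

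**4. Fibre scaling.** Kiwifruit: 2 × 150 g × 3% = 9 g/day, of which two thirds, 6 g, is soluble. Applying the 1.5-fold water-holding factor to all of it gives 13.5 g. Ispaghula: 3 × 7 g = 21 g/day, counted entirely as fibre (an assumption). The T1 effect is taken as proportional to fibre and the SD is held at 55 (also assumptions).

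| Basis | Ratio to 21 g | Difference (sec.min) | Power, n=15 | n for 90% |
|---|---|---|---|---|
| Soluble only | 6/21 = 29% | 25.1 | 37.8% | 53 |
| Total fibre | 9/21 = 43% | 37.7 | 69.5% | 25 |
| Total × 1.5 | 13.5/21 = 64% | 56.6 | 95.9% | 13 |

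The 64% is a fibre share multiplied by a water-holding factor; the plain share is 29-43%. With 77.8 as the SD, the three powers are 21%, 42% and 75%.

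**5. The same scaling with the other ispaghula dose.** At 3 × 3.5 = 10.5 g/day the ratios are 6/10.5 = 57%, 9/10.5 = 86% and 13.5/10.5 = 129%. Power at SD 55 is 91%, 99.8% and above 99.9%, so every case exceeds 90%. The Study visits section also mentions three doses on day 6. That would give 3 × 4.5 = 13.5 g (64% of 21 g, power 96%), or 20.25 g with the water-holding factor (96% of 21 g, power 99.98%).

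**6. Precision.** The 95% CI half-width at n=15 is 2.145 × 55/√15 = 30.5 sec.min. A result just short of significance could have an upper limit near 2 × 30.5 = 61 sec.min, or 69% of 88.

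**The case for a change.** The strongest case for a change does not need the fibre arithmetic. The sample-size section never says what kiwifruit is expected to do, so nobody can tell whether the true difference is likely to exceed the roughly 50 sec.min that n=15 can detect with 90% power. On the twice-daily regimen and the 7 g dose, plain fibre ratios put it below that. The expectation of similar effects in the Background concerns small bowel water and does not reach the primary endpoint. Stating the detectable difference and reporting the paired difference with its confidence interval would cost only wording.

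The gap in justification is real, and so is the arithmetic. The step from there to a trial that is too small does not hold:

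- Proportionality to fibre is assumed. The Background lists other candidate components, including fructose, actinidin and calcium oxalate crystals. Significance of Findings names the role of components beyond soluble fibre as something the comparison with ispaghula may clarify. Fixing the answer in advance to set n would assume part of what is under study.
- The 38% case drops both the insoluble fibre and the water-holding factor, although the Background credits insoluble fibre (bran) with raising small bowel water. Using both gives 96%.
- The remark about less powerful treatment contrasts kiwifruit with motility stimulants and osmotic laxatives. Ispaghula is not named there, so the sentence does not rank the two.
- No section says that a p-value of 0.05 or more will be read as no effect.

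**Conclusion.** No change follows. The plan claims power for a difference of the pilot size, and that claim is correct with a wide margin (99.99%, or 98% on the least favourable reading of the SD). What remains is that 88 sec.min is borrowed from ispaghula and no kiwifruit target is named. For a small mechanistic cross-over in healthy volunteers, using the closest in-house data and keeping 90% power down to 56% of that effect is a fair trade-off.

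The fibre-scaled powers of 38-96% are conditional on proportionality, a constant SD of 55, ispaghula counted as all fibre, and the 7 g dose. They cannot support a larger n, because the plan misses no figure that it states. Writing down the detectable difference, the source of 88 (55) or a confidence interval would help a reader but would leave the endpoint, the test and the result as they are. An analyst can report the mean paired difference with its interval in any case.

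The two ispaghula doses, and the twice-daily regimen against the three doses mentioned for day 6, are separate contradictions that the sponsor needs to reconcile. Neither alters the stated power for 88 sec.min.

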**Study Design:*****(a) Study design***

This will be a randomised, placebo controlled, 2-way cross-over study in 15 healthy volunteers. The University will allow 2 weeks between studies to ensure return to baseline. In the unlikely event that these healthy subjects' bowel habit has not returned to normal the University will extend this by 1 or 2 weeks as required.

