***(b) Study visits***

[figure not shown]
After a screening visit to confirm eligibility, study subjects will be randomised as to the test product schedule and be given the transit markers and instructions as to consume the test product two times daily for 2 days prior to the MRI study day on which they will also consume the kiwifruit as for the previous 2 days (see Figure 2). They will attend for the main imaging study on day 6 (see Figure 2).

Subjects will complete a daily stool diary documenting stool frequency and consistency using the Bristol Stool Form Scale during study days 1-6. They will visit the study site on the morning of Day 4 to receive their MRI marker capsules and kiwifruit or maltodextrin placebo. They will consume 2 kiwifruit b.d. starting on Day 4. At 9 am of the morning of Day 5 they will ingest 5 MRI transit markers as described below and note the time of ingestion. The University will contact subjects to remind them to take the pills and bring their test product packs with them as they will be required to take the same 3 doses on the study day 6. The markers will be imaged at 24 hours (baseline scan of Day 6).

On the main study day (day 6), the subjects will arrive fasted and undergo fasting scans before consuming that day's allocated test product with 250ml of water. After 30 minutes considered to be Time =0 they will consume a standard rice pudding meal as used in previous studies. They will then undergo serial scanning hourly for 8 hours taking the second dose of test product plus 250ml water at Time 180 minutes. At 380 minutes they will consume a second, larger test meal consisting of 400 g microwaveable macaroni cheese ready meal (Sainsbury), 100 g cheesecake slice (Sainsbury), and 250 mL bottled still water. The second test meal provides 1007 kcal, 43.4% from carbohydrate and 45.8% fat. The final scan will at time 420 minutes to assess the effect of ileal emptying on ascending colon water content. They will then be allowed home.

Figure 2

Study time lines

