#### **Secondary endpoints:**

Effect of Kiwifruit on the following measures both fasting and postprandial AUC 0-420 minutes:

- 1) small bowel water content
- 2) ascending (AC), transverse (TC) and descending (DC) colonic volumes
- 3) Transit of markers through gut as assessed by the weighted position score at 24 h (WAPS24)
- 4) Colonic motility
- 5) Gastric emptying of test meal
- 6) T1 of AC and DC

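### Product order is randomised in a 2-way crossover but the paired t test has no period term; adding one in the normal-data branch is a cheap safeguard, not the correction of an error

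*Combined protocol and SAP*

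**What the plan says.** Under Study Design (a) the protocol states: "This will be a randomised, placebo controlled, 2-way cross-over study in 15 healthy volunteers". It adds: "The University will allow 2 weeks between studies to ensure return to baseline", with a possible extension of 1 or 2 weeks. Under Study visits (b), "study subjects will be randomised as to the test product schedule", so order is set by randomisation.

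The primary endpoint is "Effect of Kiwifruit on Ascending colon T1 area under curve from time 0-420", which yields one value per participant per visit. The secondary endpoints are introduced as "Effect of Kiwifruit on the following measures both fasting and postprandial AUC 0-420 minutes" and include the 24-hour marker score.

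The section Power and statistical analysis names a two-way ANOVA for differences over time with corrected post-hoc tests, and then: "Paired comparisons will be performed using two-tailed Student's t test for normal, and two-tailed Wilcoxon's test for non-normal data". For an endpoint with one value per visit, the paired test is the natural reading. None of these tests is said to use order or period. The sample size rests on an ispaghula pilot that "showed a change of T1 AUC 0-360 of mean (SD) 88 ( 55) sec.min".

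**The concern.** Pairing removes stable differences between participants. It does not remove a general shift between the first and second study period, which are at least 2 weeks apart. Write P for that shift, first period minus second. The kiwifruit-minus-placebo difference then contains +P for participants who take kiwifruit first and -P for those who take it second. This has two consequences for the planned paired test:

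- the shift enters the SD of the differences and widens the confidence interval;
- if the two orders have unequal numbers, the estimate moves by (n1 - n2)/15 of P. With 15 participants exact balance is impossible.

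Precision is what is at stake. It would matter most if kiwifruit has a smaller effect than ispaghula had in the pilot, and for the secondary endpoints, for which no power calculation is given.

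**Working it through.** **Inputs.** n = 15, two-sided alpha 0.05, pilot change 88 and SD 55 sec.min, all from Power and statistical analysis. Three inputs are assumptions:

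- 55 is the SD of paired differences and excludes any period effect;
- the period effect P takes illustrative values, because the documents give none;
- a smaller true effect of 44 sec.min (half of 88) is used to show sensitivity.

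**1. The plan's own figure.** Paired t test: noncentrality = (88/55) × √15 = 6.20 on 14 df, giving power 99.99%. The claim of more than 90% is reproduced.

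**2. Cost of a period term when P = 0.**

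- Planned test: SE = 55/√15 = 14.20; 14 df; critical t 2.145; nominal half-width 30.5.
- With period: SE = (55/2) × √(1/8 + 1/7) = 14.23; 13 df; critical t 2.160; nominal half-width 30.7.
- The average half-width, which allows for the SD being estimated, is 29.9 without the term and 30.2 with it.
- Power at 88 is 99.99% either way. Power at 44 is 82.1% without the term and 81.5% with it.
- With a 10/5 split, SE = (55/2) × √(1/10 + 1/5) = 15.06, and power at 44 with the term is 77.0%.

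**3. What the planned test loses when P is not zero (8/7 split).** The expected sample variance of the paired differences is 55² + P² × 4 × 8 × 7/(15 × 14) = 3025 + 1.067 P². At P = 27.5 this is 3025 + 807 = 3832, so the SD is 61.9 and the nominal half-width is 2.145 × 61.9/√15 = 34.3. By simulation:

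| P (sec.min) | Average half-width, paired t | Average half-width, with period | Power at 44, paired t, by sign of P | Power at 44, with period |
|---|---|---|---|---|
| 0 | 29.9 | 30.2 | 82.1% | 81.5% |
| 13.75 | 30.9 | 30.2 | 82.0% / 78.6% | 81.5% |
| 27.5 | 33.7 | 30.2 | 78.4% / 70.8% | 81.5% |

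**4. Break-even.** Equate the squared nominal half-widths: 2.145² × (3025 + 1.067 P²)/15 = 30.75². The P-dependent part must equal 30.75² - 30.46² ≈ 17.7, and its coefficient is 2.145² × 1.067/15 ≈ 0.327. So P² ≈ 54 and P ≈ 7 sec.min (0.13 SD). On power at 44, averaged over the sign of P, break-even is about 8 sec.min. Below that the planned paired t is slightly better.

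**5. Validity of the planned test.** At 8/7 the estimate shifts by P/15, and a real period effect makes the paired t conservative (type I error about 3.0% at P = 27.5). At a realised 10/5 split the shift is P/3 and type I error at P = 27.5 is about 6.2%. Averaged over simple randomisation, type I error is 5.0% to 5.1% for P from 0 to 55.

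**6. The non-normal branch.** The rank analogue of a period-adjusted test is the rank-sum test on period differences. At 8/7, effect 44 and P = 0, its power against the signed-rank test is 76% v 80% for normal differences and 89% v 92% for t-distributed differences with 3 df. The two break even only near P = 20 sec.min.

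**The case against.** The strongest objection is that the gain depends on a period effect that nothing documents. Participants are healthy, T1 is read by a blinded investigator, test meals are standardised, behaviour before the test day is restricted, and the washout can be extended. This stands: none of it rules out a period effect, but the term is insurance and not an assured gain.

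A second objection concerns the SD. If the pilot was a within-person comparison and 55 is the raw SD of its differences, it may already contain a period effect, and adding P on top counts it twice. This also stands, because the derivation of 55 is not shown. It rules out relying on large scenarios such as P = 55, which would make the total SD about √(55² + 55²) = 78. It does not remove the case for the term. If 55 is the total and P = 27.5, the residual SD is √(55² - 27.5²) = 47.6. The adjusted half-width is then about 30.2 × 47.6/55 = 26.1, against roughly 30 without the term.

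Third, the rank-based equivalent is not cheap (step 6). This is accepted, and the proposal is limited to the normal branch.

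A reader might also infer that the planned test is biased or that the power claim fails. The documents do not support either. Under simple randomisation the estimate is unbiased on average and type I error is about 5%. Power at the planned 88 is above 99.9% with or without the term at 8/7 for P up to 27.5. Nor can one infer that order is unbalanced: the text available to us states no ratio or blocking, but some pages were not available.

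**Conclusion.** The point holds as a low-cost improvement. Order is randomised, the planned paired t test ignores period, and a period term would bring the analysis into line with the randomisation. It does not correct an error and does not alter the sample size.

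At an 8/7 split and a residual SD of 55, the downside is about 0.3 sec.min of half-width and 0.6 points of power at an effect of 44. The upside begins at a period effect of about 7 to 8 sec.min and reaches a 3.5 sec.min narrower half-width at 27.5. The narrowing does not depend on the size of the treatment effect; it affects power only when the true effect is well below 88. The period effects and the 44 are assumptions, the reading of 55 is uncertain, and 88 (55) itself comes from ispaghula over 0-360 minutes, not kiwifruit over 0-420. No calculation is available for the secondary endpoints, so the same gain there is plausible but unquantified.

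**What to change.** In Power and statistical analysis, for each AUC or single-value endpoint in the normal-data branch, replace the paired t test with a model containing treatment, period and participant. The same result comes from an unpaired t test comparing period-1 minus period-2 differences between the two orders, with the difference and its confidence limits halved. Report the treatment difference with its 95% CI.

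Leave the two-tailed Wilcoxon test in the non-normal branch. If a period-adjusted rank analysis is wanted, add the rank-sum test on period differences as a sensitivity analysis only.

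The cost is a few lines of text and 1 degree of freedom; no mixed-model procedure is needed. The cost in power depends on the realised split: at an effect of 44 with no period effect, it is 0.6 points at 8/7 and about 5 points at 10/5 (82.1% to 77.0%).
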